The trial is being run as a two-arm cluster randomised controlled trial with random allocation at the level of the YPSW. Each SSWs is assigned to the same group as the YPSW with which they work most frequently. The unit of analysis for the primary outcome is the YP. As is explained in more detail in the randomisation section, **the randomisation leads to a trial with four arms as follows, but only the first two of the arms are to be used in the main trial analysis**³: (i) YP where both the YPSW and SSW are assigned to the training; (ii) YP where neither the YPSW nor the SSW are assigned to the training; and (iii) YP where the YPSW is assigned to the training but the SSW is not; and (iv) YP where the SSW is assigned to the training but the YPSW is not. This document focuses on the main trial analysis of the first two arms. Analysis that incorporates all four arms is described in the final section of this document 'Analysis of all four arms of the trial'.

Data collection

Data for the trial is being collected at two points in time, at baseline (prior to randomisation of the YPSWs) and at a follow-up point 10 to 12 months later, via online surveys directed at the in-scope YPSWs and SSWs, and FCs. The SDQ data for YP is being collected via the online surveys sent to the FCs. Social Worker involvement in the trial is not dependent on FCs agreeing to complete the surveys, so there is inevitably a fairly high percentage of missing data for YPs and FCs at both baseline and follow-up. Likewise, social workers are randomised to intervention or control irrespective of whether they complete a baseline or follow-up questionnaire.

FCs will be asked to complete a follow-up questionnaire to cover their own outcomes even if their eligible YP is no longer in their care. In cases where a YP moves to another FC, the new FC will be asked to complete the SDQ at follow-up. If a YP moves out of foster care entirely they will be excluded from the trial analysis, the exception being the secondary outcomes that capture moves. Social workers will be asked to complete follow-up questionnaires even if they have changed jobs, but we expect the response rate for movers to be low.

³ As is described later in the randomisation section, this is because the four arms are not all equivalent, with the first and second arms being balanced, and the third and fourth, but without balance across between the first/second and third/fourth arms.

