where

n_1 is the achieved sample size in the intervention arm (Group 1);

n_2 is the achieved sample size in the control arm (Group 2);

m is the average cluster size;

ρ is the ICC; and

R is the correlation between the baseline and follow-up score.

The value 1.96 is the z-value for a type 1 error rate (alpha) of 0.05, and 0.84 is the z-value for 80% power.

Table 2 sets out the assumptions for the primary outcome (externalising SDQ score). The assumptions do not all hold for the secondary outcomes, the major differences being:

- For SSDA903 outcomes which are collected via administrative systems, the sample sizes will be somewhat larger because losses to the sample will be lower. The correlation between baseline and follow-up is not known but is likely to be low for the non-SDQ scores at least, and the ICC is not known, but overall we expect an MDES of around 0.20sd for these outcomes;
- There will be fewer FCs than YP in the analysis as FCs may care for more than one eligible YP, our best current assumption being that it will be around 139 in Group 1 and 163 in Group 2. We estimate an MDES of 0.27sd for their outcomes.
- There are 422 YPSWs and 264 SSWs in the trial (686 overall), divided into two groups, intervention and control, with around 316 in the intervention arm and 370 in the control arm per arm (139 and 163 respectively after non-response). For their outcomes we estimate an MDES of around 0.23sd.

Table 2: Sample size calculations

	Protocol version 1	Post randomisation
Minimum Detectable Effect Size (MDES)	0.21 sd	0.24 sd

		Protocol version 1	Post randomisation
Pre-test/ post-test correlations	level 1 (participant)	0.6	0.6
	level 2 (cluster)	0	0
Intracluster correlations (ICCs)	level 1 (participant)	0	0
	level 2 (cluster)	0.2	0.2
Alpha ⁷		0.05	0.05
Power		0.8	0.8
One-sided or two-sided?		Two	Two
Average cluster size		7.7	1.5
Number of clusters ⁸	intervention	70 YPSWs	198 YPSWs/124 SSWs at randomisation stage
	control	70 YPSWs	224 YPSWs/140 SSWs at randomisation stage
	total	140 YPSWs	422 YPSWs/264 SSWs
Number of participants	intervention	540	183 (after non-response)
	control	540	208 (after non-response)
	total	1,080	391

⁷ Please adjust as necessary for trials with multiple primary outcomes, 3-arm trials etc. when a Bonferroni correction is used to account for family-wise errors.

⁸ Please adjust as necessary e.g., for trials that are randomised at the setting, practitioner or participant level.

Analysis

Primary outcome analysis

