The characteristics shown will be: YP randomised per LA, gender, age, ethnic group, SDQ externalising mean at baseline, and SDQ internalising and prosocial score means at baseline.

Missing data

We will describe and summarise the extent of missing data per outcome, and the reasons for data being missing where known will be reported on. We will document how much missing data is unit non-response and how much is item non-response, and whether there is evidence for trial imbalance because of missing data either at baseline or follow-up.

The primary ITT regression analysis will be based on complete cases, that is those for which all of the variables needed for the model are complete. The implicit assumption here is that missing data at follow-up is 'missing completely at random' (MCAR). However, because the rate of missing data in this trial is inevitably high (because of non-response to the surveys by FCs either at baseline or follow-up), we will assess the sensitivity of the results to alternative assumptions about the mechanisms leading to missing data.

¹¹ We ruled out analysis that tries to control for these switches because we will not have rich enough data to know when during the trial period the switch occurred, and because of the additional complexity introduced because both or just one of the professionals could be switched

Firstly, we will use the baseline outcome variables for YP and FCs¹², together with other YP and FC characteristics to model (via a logistic regression) the probability per YP of a case being in the intervention arm rather than the control arm. This will identify any observable predictors of imbalance, and the regression model (Eq 1) will be re-run to include, as covariates, any significant predictors that are identified from this logistic regression. This will help establish whether the effect sizes are influenced by the level and nature of missing data, under an assumption of missing at random (MAR).

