Secondly, we will make use of the fact that the SSDA903 data will provide total SDQ scores at baseline and follow-up for many of the young people in the trial, the main exceptions being those young people who have been looked-after continuously for less than 12 months and those aged 17¹³. We will test whether there is evidence of non-response bias in the trial by comparing the mean SSDA903 scores for respondents and non-respondents at each time point, separately within each arm of the trial. If there are observed differences in the means this will allow for an estimate of the magnitude and direction of any bias.

Finally, if there is evidence that outcomes data is missing not at random (MNAR) we will include some estimates of effect sizes based on a range of extreme assumptions about the missing outcomes. This will generate upper and lower bounds for the effect sizes. The assumptions adopted for this sensitivity analysis will include imputing the worst possible outcomes scores for those missing from the intervention arm and the best possible outcomes scores for those missing from the control arm.

The approach will be repeated across all of the secondary outcomes with the probable exception of the SSDA903 outcomes, where we do not anticipate much missing data.

Compliance

Defining 'compliance' for YP in the trial is not straightforward because of the fact that the intervention is being delivered to social workers rather than to the YP themselves, so YP 'compliance' is dependent on the decisions of their YPSWs and SSWs. Because YP may change their YPSW, and their FCs may change their SSW, between baseline and follow-up, compliance

¹² FC baseline data will be used in the model because it is FCs who complete the data about YP.

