¹³ The SDQ scores from the SSDA903 will not be affected by attrition so the sample sizes will be larger and non-response bias less likely. However, it is being used as an outcome measure in its own right for a range of reasons. The SDQ recorded in the SSDA903 excludes YP who are over 16 and only includes YP who have been looked-after continuously for at least 12 months. Also, the timing of the data collection can vary during the year, so the data is not at a fixed outcome point. Experience on other studies (in particular the evaluation of the Mockingbird programme) has been that SDQ data is often missing from SSDA903 submissions which would reduce its usefulness. However, early indications on the current trial are that it is close to complete.

is not a binary variable per YP per social worker. Furthermore, a control group YP could, during the trial, be re-assigned to a YPSW or SSW who is in the intervention arm (and vice versa), further complicating the definition of compliance.

Compliance with the training for social workers will be defined as a binary variable. The definition of compliance to be used is attendance of 4 out of 7 training sessions plus 2 out of 3 reflective practice sessions. In light of this, we will define compliance for YP in the intervention group as that one or both of their YPSW and SSW at baseline are compliant with the training.

The problem of YP being re-assigned to a social worker from the opposite arm of the trial is likely to be unrelated to the trial itself, so it seems reasonable to assume it will affect both of the primary analysis arms of the trial equally. In light of this, we will run a CACE analysis to isolate the impact of compliance with the training after excluding these switched-arm cases from the data.

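### The missing-data checks extended to ARTIC are built on young-person data and would not show whether social worker response depends on training attendance

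*SAP*

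**What the plan says.** The Missing data section of the SAP takes complete cases as the main analysis, acknowledges that this implies data missing completely at random, and sets three sensitivity steps.

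1. A logistic regression is used "to model (via a logistic regression) the probability per YP of a case being in the intervention arm" from young person and foster carer baseline variables. Significant predictors are then added to Eq 1.
2. Young people's SDQ totals in the SSDA903 are compared between respondents and non-respondents, within arm and at each time point.
3. If there is evidence of data missing not at random, bounds are computed from extreme values.

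The section closes: "The approach will be repeated across all of the secondary outcomes with the probable exception of the SSDA903 outcomes". ARTIC is therefore included.

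ARTIC is measured on social workers and analysed with its own model, Eq 3 (follow-up ARTIC on arm, baseline ARTIC and local authority). The sample size section puts the social workers at "around 316 in the intervention arm and 370 in the control arm per arm (139 and 163 respectively after non-response"), and adds: "For their outcomes we estimate an MDES of around 0.23sd". On social workers who change jobs, the Data collection section says "we expect the response rate for movers to be low".

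Attendance appears in the Compliance section: "Compliance with the training for social workers will be defined as a binary variable". The rule is 4 of 7 training sessions plus 2 of 3 reflective sessions. It feeds the young-person compliance measure and a separate CACE analysis for ARTIC. The Missing data section does not mention it.

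**The concern.** RQ6 is the only outcome measured on the people who were trained, so it will be used to interpret whatever the primary outcome shows. About half of these workers are expected to be absent from its analysis.

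The training runs over five months. A worker who leaves or disengages in that time may attend fewer sessions and also be less likely to answer the follow-up survey. If so, the intervention-arm responders contain too many attenders. Complete-case Eq 3 would then estimate the effect in that enriched group and report it as ITT. Adjusting for baseline ARTIC does not remove this, because attendance arises after randomisation. The SAP does not state that attenders respond more often. It is a reasonable possibility, and the plan should be able to detect it.

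**Working it through.** **The three steps applied to ARTIC**

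- Step 1: the unit is the young person, the predictors are young person and carer variables, and the model re-run is Eq 1. ARTIC has another unit and another model. Even with baseline ARTIC, role and local authority substituted, the step looks for baseline predictors of arm. It cannot show response depending on attendance, which arises after randomisation and only in the intervention arm.
- Step 2: the SSDA903 is a return on looked-after children. It holds no score for a social worker.
- Step 3: it needs evidence of data missing not at random, and steps 1 and 2 give none for social workers. If run anyway at the printed counts, the missing fractions are 1 − 139/316 = 0.560 and 1 − 163/370 = 0.559. The two extreme scenarios then lie 0.560 + 0.559 = 1.12 full scale ranges apart, which is uninformative.

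**How much is missing**

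The SAP's formula is MDES = 2.8 × √[(1/n₁ + 1/n₂)(1 + (m − 1)ρ)(1 − R²)].

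- Primary outcome (183 and 208, m = 1.5, ρ = 0.2, R = 0.6): 0.238, stated 0.24.
- Foster carers (139 and 163, m = 1.5, ρ = 0.2, R = 0.6): 0.271, stated 0.27.
- Social workers (139 and 163, no clustering, R = 0.6): 0.259, stated 0.23. This does not reproduce. At these counts 0.23 needs R of about 0.70, and the SAP gives no R for ARTIC.

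The pair 139 and 163 is also the foster carer pair, so it may have been carried over. Two readings follow.

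- Printed counts right: 302/686 = 44% analysed, 56% missing.
- 0.23 sd right with R = 0.6: 1/n₁ + 1/n₂ = 0.23²/(2.8² × 0.64) = 0.01054. In the ratio 316:370 this is about 382 workers, so 44% are missing.

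**What attendance-related response could do**

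Nothing in the SAP fixes these inputs; they are assumptions for illustration. Let 60% of intervention workers meet the attendance rule, with an effect of 0.5 sd in them. The attender share among responders is 0.6 × r_A / (0.6 × r_A + 0.4 × r_N), where r_A and r_N are the response rates of attenders and others.

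| Response, attenders / others | Effect in others | Attender share | True ITT | Complete case | Excess |
|---|---|---|---|---|---|
| 60% / 20% | 0 | 0.36/0.44 = 0.818 | 0.30 | 0.41 | 36% |
| 60% / 20% | 0.25 sd | 0.818 | 0.40 | 0.455 | 14% |
| 50% / 35% | 0 | 0.30/0.44 = 0.682 | 0.30 | 0.34 | 14% |
| 85% / 65% | 0 | 0.51/0.77 = 0.662 | 0.30 | 0.33 | 10% |

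The last row allows for loss before randomisation. Eq 3 also needs baseline ARTIC, collected before randomisation, and loss at that stage does not bias the arm comparison. If baseline response were 57% (the SAP's figure for young people, borrowed here), follow-up response would be 0.44/0.57, about 77%. A threefold response gap could not then occur: with all attenders responding, the others would respond at (0.77 − 0.60)/0.40 = 0.425, a ratio of about 2.4.

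In 3,000 simulated trials of the first row (316 and 370 workers, baseline correlation 0.6), complete-case Eq 3 averaged 0.408 (SD 0.096). Standardising the intervention arm to its full attendance distribution averaged 0.298 (SD 0.104). The recovery is by construction, since response was made to depend only on attendance. The useful result is the cost in precision: 0.104/0.096, about 8%.

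**The case against.** The strongest reply is that repeating the approach means adapting it to each unit, as the SAP does when it re-specifies Eq 1 as Eq 3. The section also promises a description of missing data for every outcome, with reasons where known, and the bounds need no young-person data. All of this stands. A reader might infer that ARTIC has no check at all, and the text does not support that. The adaptation is not written down, however. Its natural form still could not reveal attendance-related response, and the bounds are conditional and too wide to inform.

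A reader might also infer that attendance is not used anywhere. It is, for compliance and for the ARTIC CACE. The CACE estimates an effect in compliers and does not repair the ITT estimate.

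Extending the point to the foster carer outcomes is tempting but not supported. Step 1 already uses carer baseline data. Carers also supply both the SDQ and their own scales in the same surveys, so comparing SSDA903 SDQ scores for responding and non-responding carers gives indirect evidence.

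Finally, 36% should not be read as the expected bias. It assumes that all loss is after randomisation and related to attendance, with no effect below the attendance threshold. The objection on size stands in full.

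**Conclusion.** The SAP applies to ARTIC a set of checks that, as written, do not describe social workers, and it leaves attendance out of the assessment of missing data. Expected missingness is between about 44% and 56%. The lower figure assumes R = 0.6 for ARTIC and that 0.23 sd is the correct MDES; the upper takes the printed counts at face value.

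Whether complete-case Eq 3 is biased, and by how much, cannot be known from the document. The illustrations run from about 10% to 36% too high. They depend on the response gap between attenders and others, the effect in non-attenders, and how much loss occurs before randomisation. If response is unrelated to attendance, this source of bias is absent. The point concerns one secondary outcome; the primary result is unaffected.

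**What to change.** For ARTIC, replace the closing sentence of the Missing data section with two specified steps.

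- (a) Within each arm, compare follow-up responders and non-responders on baseline ARTIC where available, role, local authority and job change where known. In the intervention arm, also compare sessions attended.
- (b) Always run one sensitivity analysis in which missing follow-up ARTIC is imputed by arm from baseline ARTIC, role and local authority, plus sessions attended in the intervention arm. An attendance-standardised estimate would serve equally. State how workers without a baseline score are handled, and that the analysis assumes data missing at random given these variables. This should not be left to the conditional worst/best bounds alone.

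Attendance must be known for workers who do not answer the survey, because young-person compliance is defined from it. The SAP does not name the source, so confirm that the records cover non-responders. In the same edit, reconcile 139 and 163 with 0.23 sd, and reconcile 316 and 370 with Table 2, whose cells sum to 198 + 124 = 322 and 224 + 140 = 364.

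The cost is SAP wording, one table and one extra model. The interval for the sensitivity estimate will be slightly wider (about 8% in the example).

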	measure (instrument, scale, source)	
Young person: SDQ, carer-report version; Child conviction or subject to youth caution (SSDA903 2023-2024); transition into residential care (SSDA903 2023-2024); unplanned moves (SSDA903 2023-2024); missing from care episodes (SSDA903 2023-2024)
 
SSW / YPSW: ARTIC Scale prior to randomisation
 
FCs: Professional Quality of Life Scale (self-report); bespoke questionnaire (self-report) as close as possible to randomisation of YPSW

Randomisation

There are constraints on the number of training places per LA⁴, so YPSWs per LA have not typically been allocated to intervention and control group in the ratio 50:50. Instead, the percentage allocated to the intervention was set so that all available places were filled, with up to a maximum of 70% being allocated to the intervention. In practice, for most LAs, the percentage allocated to the intervention was around 46%. Randomisation was run separately per LA by the trial statistician, giving implicit stratification by LA. Since the trial statistician is undertaking the randomisation and will conduct the statistical analysis, the analysis will not be blind to allocation.

A significant complication in this trial is that the primary analysis aims to test whether delivering the intervention to both SSWs and YPSWs improves outcomes for YP, rather than simply testing whether delivering the intervention to one set of professionals or the other has an impact. Yet, SSWs do not cluster within YPSWs (or vice versa), so straightforward randomisation of YPSW/SSW pairs is not feasible. Inevitably some young people in each LA will have a SSW who has been assigned to the intervention group and a YPSW who has been assigned to the control group, and vice versa. That is, when the randomisation is complete, there will be YP in each of four arms, with the first two (in bold) being the primary analysis arms:

⁴ Depending on the number of in-scope social workers in an LA, either one or two training groups were allocated to the LA, with the maximum number of places per group being 35.

Arm 1: T_{SSW}T_{YPSW} (i.e. both SSW and YPSW assigned to the intervention);

Arm 2: C_{SSW}C_{YPSW} (i.e. both SSW and YPSW assigned to the control group);

Arm 3: T_{SSW}C_{YPSW} (i.e. SSW assigned to the intervention and YPSW assigned to the control group);

Arm 4: C_{SSW}T_{YPSW} (i.e. SSW assigned to the control group and YPSW assigned to the intervention group).

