The analysis of the efficacy trial data will be on an intention-to-treat basis. Estimates of impact per outcome will be based on a multilevel linear regression model with two levels, YPSW and YP, with the baseline version of each outcome being entered as a covariate. LA will be entered as a fixed effect. The analysis will be conducted in SPSS v28.0.1.1 via the MIXED procedure.

If, after non-response, we have data that is essentially unclustered then a single-level model will be fitted.

Primary outcome analysis

The primary outcome measure for YP in the trial is the SDQ externalising score.

The SDQ questionnaire includes five subscales, each with five items, that measure: 1. Emotional symptoms; 2. Conduct problems; 3. Hyperactivity/inattention; 4. Peer problems; 5. Prosocial behaviour. FCs score from 0 to 2 on each item using a scale 'not true', 'somewhat true' or 'certainly true', thus producing a score for each subscale from 0 to 10, where a lower total score is a better outcome for subscales 1-4, and the reverse for subscale 5 (prosocial behaviour). The 'externalising' score (from 0 to 20), is generated by summing the scores of the conduct and hyperactivity subscales.

The calculation of the externalising score will follow the standard SDQ scoring rules. The score will only be calculated where both subscales have a valid score (that is, at least three of the five items have been answered), others being set to missing. Each subscale will be calculated as (total subscale score)*5/(number answered).

The main regression model specification is as follows:

$$Y_{ijk} = \beta_0 + \beta_1 \text{Group}_{jk} + \beta_2 X_{ijk} + \beta_3 LA_k + u_{ijk} + \varepsilon_{ijk} \quad (\text{Eq 1})$$

where

Y_{ijk} = externalising score at follow-up for young person i belonging to assigned at baseline to YPSW j within LA k;

$\beta_0, \beta_1, \beta_2, \beta_3$ = fixed effect parameters;

Group_{jk} = indicator variable for group allocation of the YP's YPSW and SSW (0=control; 1=intervention) within LA k;

X_{ijk} = baseline externalising score for young person i assigned at baseline to YPSW j within LA k;

LA_k = a vector for the local authority dummy variables, of which there will be seven. β_3 is a coefficient vector for the LA dummy covariates;

u_{ij} =random effect for i th member of YPSW j ;

ε_{ijk} = residual error term for i th member of cluster j .

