We will re-run the ITT primary outcome regression model to generate the ITT effect size for this reduced dataset. Complier Average Causal Effect (CACE) will then be used to estimate the effect size for the 'social worker compliers' (as defined above). This will be estimated using two stage least squares (2SLS) regression. The first stage will model the compliance variable using the same explanatory variables used for the headline ITT analyses. This will be a multilevel logistic regression model used to generate predicted compliance for use in the second stage model. The second stage models will use predicted compliance in place of the group identifier variable in the ITT analyses specified above to generate the CACE estimate.

A separate CACE analysis will be conducted for the secondary social worker outcome, ARTIC.

Intra-cluster correlations (ICCs)

The trial is clustered within YPSWs. For the YP primary and secondary outcomes, ICCs will be presented, calculated at pre and post-test as the between-cluster variance divided by the total variance from the regression models. In addition, for the post-test, the ICC using the variance components from the adjusted regression model will be presented.

Presentation of outcomes

Effect sizes will be calculated using Hedges' g , as specified in the following equation:

$$ES = \frac{(\underline{Y}_T - \underline{Y}_C)_{adjusted}}{s}$$

where \underline{Y}_T is the regression adjusted mean for the treatment group, \underline{Y}_C is the regression adjusted mean for the control group (computed using Eq 1), and s^2 is the pooled unconditional variance of the two groups (derived from the raw data).

Effect sizes will be reported along with confidence intervals and p-values to reflect statistical uncertainty.

Analysis of all four arms of the trial

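### The CACE is called 2SLS but has a multilevel logistic first stage, so it can drift towards an as-treated comparison or towards the ITT

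*SAP*

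**What the plan says.** The SAP's Compliance section names the estimator: "This will be estimated using two stage least squares (2SLS) regression". On stage one it says: "The first stage will model the compliance variable using the same explanatory variables used for the headline ITT analyses". From Eq 1 these are Group, the baseline score and the LA dummies. The form of stage one is then given: "This will be a multilevel logistic regression model used to generate predicted compliance for use in the second stage model". On stage two: "The second stage models will use predicted compliance in place of the group identifier variable in the ITT analyses specified above". The ITT model into which the prediction goes is linear: "Estimates of impact per outcome will be based on a multilevel linear regression model with two levels, YPSW and YP" (Analysis, Primary outcome analysis).

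Compliance is a property of the workers, carried over to the young person: "we will define compliance for YP in the intervention group as that one or both of their YPSW and SSW at baseline are compliant". Arm 2 is the group with "both SSW and YPSW assigned to the control group" (Randomisation), and the CACE is run "after excluding these switched-arm cases from the data".

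The SAP does not say whether the first-stage predictions include the YPSW random effect, how control compliance is coded, or how the CACE standard error is obtained.

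**The concern.** In 2SLS the first stage is a linear regression. Its residual is uncorrelated with allocation and the covariates by construction, so the second stage uses only the part of compliance that allocation, baseline score and LA predict. That is what protects the estimate when workers who attend differ from those who do not.

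A multilevel logistic prediction lacks this property, and what it brings into the second stage depends on the random effect:

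- **Random effect included.** The YPSW effect is estimated from who actually complied. Since compliance is set by the workers, the prediction largely reproduces observed compliance, and the second stage moves towards comparing young people by whether their workers attended.
- **Random effect set to zero.** The prediction is the compliance probability of a typical YPSW, which differs from the average compliance rate, so the scaling of the ITT is wrong.

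At stake is the label. The result would be read as a complier effect that rests on randomisation, while its size would depend on a choice made at analysis by a statistician who, as the Randomisation section says, is not blind to allocation.

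**Working it through.** **1. Inputs.** From the Sample size calculations overview and Table 2: 183 intervention and 208 control YP, mean cluster size 1.5, ICC 0.2, baseline to follow-up correlation 0.6. These reproduce the stated MDES: 2.8 × sqrt((1/183 + 1/208) × (1 + 0.5 × 0.2) × (1 - 0.36)) = 0.238, stated as 0.24. With correlation 0.53 the formula gives 0.252, stated as 0.25.

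The SAP gives no CACE figure and no expected compliance rate. Assumed here: a true complier effect of -0.30 sd (negative is benefit), compliance of 60% to 70%, and would-be compliers having untreated outcomes 0.3 sd better.

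**2. Target.** With no compliance among controls, CACE = ITT / p, where p is compliance in the intervention arm. An ITT of 0.24 sd corresponds to 0.48, 0.40, 0.34, 0.30 and 0.27 sd at p = 0.5, 0.6, 0.7, 0.8 and 0.9.

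**3. Separation.** Control YP have two control workers and switched cases are removed, so control compliance is 0. In a logistic fit to such data (no random effect) the Group coefficient was 7.3, 12.3, 22.3 and 32.3 after 5, 10, 20 and 30 iterations, and its standard error rose from 1.1 to about 300,000. The largest fitted control probability fell from 0.0017 to below 10^-13. The coefficient has no finite estimate, but the control predictions go to the correct value.

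**4. Random effect set to zero.** If the prediction is about p0 in the intervention arm and 0 in control, stage two returns ITT / p0, which is the CACE multiplied by p / p0. At p = 0.70, random-effect SDs of 1, 2 and 4 on the logit scale give p0 = 0.735, 0.800 and 0.908, hence factors 0.95, 0.88 and 0.77. The pull is towards the ITT when compliance exceeds 50%; at 50% the factor is 1.

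**5. As-treated limit.** If the prediction equals observed compliance, the bias is the confounding multiplied by (1 - share of would-be compliers among the untreated).

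- At 70%: untreated = 0.3 × 183 + 208 = 262.9; would-be compliers among them = 0.7 × 208 = 145.6; share 0.554; bias = -0.30 × 0.446 = -0.134; estimate -0.43.
- At 60%: untreated = 0.4 × 183 + 208 = 281.2; would-be compliers = 124.8; share 0.444; bias = -0.30 × 0.556 = -0.167; estimate -0.47.

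**6. Simulation.** 250 trials per scenario. The random-intercept logistic model was fitted in the intervention arm with control predictions at 0 (the limit under separation), and stage two was ordinary least squares with baseline score and LA. True effect -0.30; Monte Carlo standard errors about 0.01.

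| Scenario | Linear 2SLS | As-treated | Random effect included | Random effect zero | Averaged over random effect |
|---|---|---|---|---|---|
| YPSW alone decides, 60% compliant, confounding 0.3 sd | -0.29 | -0.46 | -0.46 to -0.48 | -0.23 | -0.30 |
| YPSW 50%, SSW 40%, either suffices (1 - 0.5 × 0.6 = 70%), confounding 0.3 sd | -0.29 | -0.43 | -0.40 to -0.41 | -0.26 | -0.30 |
| As above, no confounding | -0.29 | -0.29 | -0.31 to -0.33 | -0.26 | -0.29 |

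Within the intervention arm, predictions with the random effect correlated 0.998 with actual compliance in the first scenario (where the random-effect SD reached the limit allowed in the fit) and 0.85 in the second.

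A separate refit at about 70% compliance and 0.3 sd confounding gave -0.41 to -0.44 with the random effect (as-treated -0.43), -0.22 to -0.25 with it at zero, and -0.29 for linear 2SLS. With no confounding it gave -0.33 with the random effect against -0.32 for linear 2SLS.

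**The case against.** The strongest reply is that the problem is conditional and sits in a supplementary analysis. The shift towards as-treated needs predictions that carry the random effect and attendance that is related to outcome. Predictions averaged over the random effect were unbiased. The SSW route to compliance means that YP under one YPSW can differ. The SAP also re-runs the ITT on the same reduced dataset, so the reader will see the numerator of the ratio estimate. All of this stands. It limits the point but does not remove it: under the SAP's own compliance rule the random-effect version still came close to as-treated.

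A reader might infer more than the SAP supports:

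- **That separation corrupts the CACE.** It does not. Stage two uses predictions, and the control predictions go to 0. Zero control compliance is itself inferred from the definitions, since the SAP never codes it.
- **That a logistic form in itself causes material bias.** In 2,000 simulated trials with fixed-effects logistic predictions and a true effect of -0.24, the plug-in gave -0.237 against -0.236 for linear 2SLS; with compliance grossly non-logistic in baseline score, -0.241 against -0.240.
- **That the intervals will be too narrow.** The SAP states no standard-error method for the CACE. In the same simulations the uncorrected clustered standard error was 0.139 against an empirical SD of 0.136 with confounding, and 0.133 against 0.132 without. Standard errors under random-effect predictions were not examined.
- **That the effect will be overstated by a fixed proportion.** The direction and size depend on the prediction type, the compliance rate and the sign and strength of the confounding.
- **That the random-effect problem reaches ARTIC.** Eq 3 has no cluster level, and no first stage is given for that CACE.

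**Conclusion.** The point holds in this form. The specified procedure is not the 2SLS that the SAP names, and two of the three natural ways to carry it out give a biased complier effect. Under the assumptions of about 70% compliance, 0.3 sd confounding and a true effect of -0.30 sd, these two ways give about -0.41 to -0.44 and -0.22 to -0.25, where linear 2SLS gives -0.29. The compliance rate, the confounding and the complier effect are assumptions, because the SAP supplies none of them. Without confounding the random-effect version is close to linear 2SLS (-0.33 against -0.32 in the refit). The primary ITT result is untouched, but a better method is available at almost no cost, so this is more than a missing detail.

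**What to change.** In the Compliance section:

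- Delete the multilevel logistic first stage.
- State that compliance is coded 0 for every control YP in the CACE dataset.
- Specify linear 2SLS with allocation (Group) as the instrument for compliance, and baseline score and LA dummies in both stages, fitted in one instrumental-variable routine with standard errors clustered on YPSW. Name the routine, since the MIXED procedure cited for the ITT models is not one. Alternatively, divide the ITT effect by the difference in compliance between arms and take the interval from a bootstrap that resamples YPSW clusters.
- State that the ARTIC CACE uses the same linear 2SLS form.

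The cost is a few sentences in the SAP and the use of a standard routine in place of a two-step calculation. No new data are needed, and the change should be made before the CACE is run.
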